9.3 Protocol Deviations and Violations

Protocol deviation data will be entered into the Clinical Trials Management System (CTMS). The study team will conduct on-going reviews of the protocol deviation data from CTMS.

Important protocol deviations (IPD) are a subset of protocol deviations that might significantly affect the completeness, accuracy, and/or reliability of the study data or that might significantly affect a subject's rights, safety, or well-being.

The protocol deviation/violation (PDV) list will be finalized prior to the database freeze, and based on the PDV data entered into CTMS, the IPD will be listed and tabulated using incidence by deviation type.

9.4 Treatments

9.4.1 Drug Exposure

Summary statistics will be provided for total duration (days) of study drug exposure and treatment compliance for the safety population.

Total duration of study exposure in days is defined as (last dose date - first dose date+1).

The total duration of study exposure will also be summarized categorically by 4 week intervals; less than 4 weeks, 4(inclusive) to 8 (exclusive) weeks, and so on. The number of weeks will be derived as (total duration of study exposure/7).

For all 3 cohorts study medication compliance with the protocol will be calculated as (100*total number of days subject took their study medication/total duration of study exposure).

The total number of days the subject took their study medication will be determined by subtracting the days the subject didn't take their medication (as reported by the dose diary or CRF pages for clinic visits) from the duration of study exposure. Days where a subject was instructed not to take their dose, recorded in the eCRF (patient dose regimen), should be excluded from the calculation of compliance; if a subject is instructed by the site to not take their dose it isn't a compliance issue.

Additionally, for Cohorts 1 and 3, compliance will also be assessed from the planned weights of IMP used. Compliance will be calculated as $100 \times \text{weight used (added across bottles dispensed)} / (\text{total duration of study exposure} \times \text{weight per day})$

Weight of bottles is recorded in g. Each day the subject should be taking 5g (if they haven't had a dose reduction) – i.e. 2 doses of 2500mg.

As every 1g of IMP contains 200mg of SMT C1100 the planned weight of medication is calculated as follows:

Planned weight of medication = $(1000/200) \times \text{Number of days} \times \text{Daily dose}$

If the subject changes their dose, then appropriate adjustments are required for their duration on each dose level. Similarly, an adjustment should be made if a subject is instructed not to take their dose.

If bottles are not returned the subject's compliance should be provided as a range – the lower value assuming they took none of the material from these bottles and the higher value assuming they used all of it.

Subjects will be considered compliant with the protocol if they take $\geq 80\%$ of their medication as scheduled. The compliance values derived by the above two approaches will also be summarized categorically by groups of 'less than 80%', 'greater or equal to 80% but less than 95%' and 'greater than or equal to 95%'.

A subject listing of study drug accountability, dosing diary, in-clinical visit dosing and study medication compliance will be provided.

Dose regimens will be detailed in a listing. The listing will detail the dosing regimen start/stop study days and duration. The number of subjects with a dose reduction, dosing regimen change, temporary cessation of treatment or permanent cessation of treatment will be tabulated.

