8.7. Product Accountability and Assessment of Compliance

In accordance with GCP, each study centre will account for all supplies of SMT C1100 provided to them. Details of receipt, storage, assembly and return will be recorded. The unit of accountability will be one bottle of SMT C1100.

All unused supplies of SMT C1100 will either be destroyed or returned to the study Sponsor at the end of the study in accordance with instruction by the Sponsor.

Patients will be counted as compliant with the protocol if they take ≥95% of their medication as scheduled.

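### Diary-based compliance counts every day without a dosing record as taken, so the reported percentage is always the upper bound of what the records allow

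*SAP*

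**What the plan says.** For all three cohorts, SAP 9.4.1 says that "study medication compliance with the protocol will be calculated as (100*total number of days subject took their study medication/total duration of study exposure". Its denominator is a calendar span: "Total duration of study exposure in days is defined as (last dose date - first dose date+1". The numerator comes by subtraction, removing the days the boy did not "take their medication (as reported by the dose diary or CRF pages for clinic visits) from the duration of study exposure". The only days set aside are those on which the site told him not to dose, which "should be excluded from the calculation of compliance". Nothing is said about a blank diary day or a diary that is not returned.

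A second measure exists for two cohorts: "Additionally, for Cohorts 1 and 3, compliance will also be assessed from the planned weights of IMP used". Where bottles are not returned, that measure is reported between two bounds: "the lower value assuming they took none of the material from these bottles and the higher value assuming they used all of it".

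The results are then classified. In the SAP, "Subjects will be considered compliant with the protocol if they take" at least 80%, and values are grouped as below 80%, 80% to below 95%, and 95% or more. Protocol 8.7 draws the line elsewhere: "Patients will be counted as compliant with the protocol if they take ≥95% of their medication as scheduled". That mismatch needs reconciling but is a separate matter.

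**The concern.** A missed dose can lower the score only if somebody recorded it. Everything unrecorded enters the numerator and the denominator as a dosed day. Incomplete diaries can therefore only raise the figure or leave it unchanged, never lower it. The missing-value counts in SAP 9.1 would not reveal this, because the boy still has a compliance value.

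This runs against the SAP's own habits. Section 9.4.1 bounds the same kind of gap for bottles, and section 5.4.1 resolves gaps cautiously, treating a missing causality as related and a missing severity as severe.

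Dosing is at home by a parent, in an open-label study without a control group. A reader will look at the compliance table to judge whether the drug was taken. Cohort 2 relies on this formula most, because no bottle-weight percentage is planned for it.

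**Working it through.** The documents state no compliance result to reproduce, so the check applies the SAP 9.4.1 formula directly.

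**Inputs.** D = exposure days after removing site-instructed days; 48 weeks × 7 = 336 (protocol 8.1). U = days with no diary or clinic record. R = days reported as missed. U and R are assumptions, because the documents give neither diary coverage nor adherence.

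**Formulas.**
- SAP value = 100 × (D − R)/D.
- What the records establish: at least D − U − R and at most D − R days taken, so the range is 100 × (D − U − R)/D to 100 × (D − R)/D.
- The SAP value equals the upper end for every U. The range is 100 × U/D points wide.

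**Illustration**, with about 30% of the recorded days reported as missed:

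| U | R | SAP value | Range | Recorded days only |
|---|---|---|---|---|
| 0 | 101 | 69.9% | 69.9% to 69.9% | 69.9% |
| 84 | 76 | 77.4% | 52.4% to 77.4% | 69.8% |
| 168 | 50 | 85.1% | 35.1% to 85.1% | 70.2% |
| 252 | 25 | 92.6% | 17.6% to 92.6% | 70.2% |
| 336 | 0 | 100% | 0% to 100% | undefined |

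**General form.** Let m be the true share of days missed, equal on recorded and unrecorded days, and c the share of days with a record. The SAP value is 1 − m × c, the truth is 1 − m, and the error is m × (1 − c).
- m = 0.30, c = 0.50: 1 − 0.15 = 85% against 70%, an error of 15 percentage points.
- c = 1: the error is zero.
- At 70% true adherence, the SAP value reaches 80% when 0.30 × c ≤ 0.20, so c ≤ 2/3: one third of days (112 of 336) uncovered. It reaches 95% when c ≤ 1/6: 280 of 336 days uncovered.
- At 75% true adherence, 80% is reached when c ≤ 0.80, with one fifth of days uncovered.

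**Clinic records.** The schedule for Cohort 2 has eight visits with dosing (Days 1 and 7; Weeks 4, 8, 12, 24, 36 and 48), and 8/336 = 2.4% of days. Suppose a boy returns no diary and all eight visits show dosing. The SAP value is 100% and the range is 2.4% to 100%. A recorded-days-only value would be 8/8 = 100%, so changing the denominator to recorded days does not cure the problem.

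**The case against.** **The diary may record missed doses only.** In that design a blank day in a returned diary means dosed, and the subtraction is right for that period. The diary layout, the CRF and the Data Management Plan are not among the documents, so this cannot be excluded. The point stands for returned diaries. It does not reach a diary that never came back, which still scores as fully dosed.

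**Little depends on the figure.** This also stands. There is no per-protocol set: the ITT and Safety populations are all dosed boys, and the endpoint populations depend on having an assessment (SAP 6.2 to 6.4). The relationship plots use plasma exposure (SAP 9.10.1). A reader might infer that the formula undermines the concentration-response work or a comparison of Cohort 2 with Cohort 1. The documents do not support that: the SAP feeds compliance into no other analysis, and efficacy and leg MRI tables pool the two cohorts (SAP 9.6.1, 9.7.1).

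**Cohort 2 is not unobserved.** F6 is supplied as unit doses and returned for accountability (protocol 8.4); accountability and diary data are listed by subject (SAP 9.4.1); plasma samples are scheduled at eight visits, with counts below the quantification limit summarised by cohort (SAP 5.5, 9.9). It would be too strong to say that nothing else bears on adherence there. What is true is narrower: no other compliance percentage is derived.

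**The size is hypothetical.** Agreed. A reader might also infer that families who miss doses are the ones who leave diaries blank, so that poor adherence is in fact being hidden. That is plausible, but nothing in the documents shows it.

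**Conclusion.** The point holds as a fault in a descriptive measure. As written, the diary formula returns the upper bound whenever dosing records are incomplete, while the bottle measure in the same section is properly bounded. Only the compliance summary and its three categories are affected. Cohort 2, about 10 boys, has no second percentage to set beside it; in Cohorts 1 and 3, about 30 + 15 = 45 boys, the bottle-weight measure partly offsets the problem.

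The direction of error is upward or nil; the size is unknown. The 15-point example assumes 30% of days missed, half of days unrecorded and equal adherence on both. A score of exactly 100% for a boy with no diary also requires that his clinic-visit pages report no missed day. The documents do not show that compliance in this trial was overstated, only that the planned table could not reveal it.

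**What to change.** In SAP 9.4.1:

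1. For days covered by neither a returned diary nor a clinic dosing record, report compliance as a range: the lower value treats those days as not taken, the upper value as taken. This is the rule already used for bottles.
2. Tabulate the below 80%, 80% to below 95%, and 95% or more categories at both bounds. Do not base them on recorded days alone.
3. Tabulate, by cohort, the percentage of exposure days covered by a returned diary or clinic record.
4. If the diary captures only missed doses, define coverage by returned-diary periods, so that a blank day inside a returned diary still counts as taken.

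The cost is SAP wording and a little programming on data already planned for listing. The downside is that stated compliance becomes less favourable or less precise. If diaries prove complete, the coverage table shows it and the two bounds coincide.

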9.4.2 Prior and Concomitant Medications/Procedures

Prior/concomitant medications will be summarized by Anatomic Therapeutic Classification (ATC) class and preferred name. The analysis will be performed using the Safety population. Summaries will be presented for all medications and also specifically for steroids taken for DMD. The summaries will include the steroids taken for DMD by boys participating in the FOR-DMD study (recorded in DMD history page of eCRF); their data will be presented in a separate listing.

The numbers (%) of subjects using each medication will be displayed. Subjects taking more than one medication in the same ATC class or preferred name will be counted once for the number of subjects taking that preferred name.

Medications will be split into two groups, by clinical review; those taken specifically for the anaesthetics related to the biopsy procedure and all others. Separate listings will be generated for each group.

Separate concomitant medication summaries (all medications and steroid medications) will be generated for the first 24 weeks, first 48 weeks and for the whole study.

9.5 Demographic and Baseline Characteristics

Demographics, baseline disease characteristics, baseline measurements will be summarized using descriptive statistics for continuous variables and frequency distributions for discrete variables, using the Safety population.

Demographics will include:

- Age (Age at screening is recorded, but age on Day 1 of dosing will be derived* and summarized in the demography summary table. The subject's age on Day 1 will also be presented, as an integer, in subject listings).
- Race
- Country
- Ethnicity
- Weight
- Height
- BMI
- Lean body mass (using Peter's formula = $3.8 \times \text{eECV}$, where estimated Extracellular Fluid Volume (eECV) = $0.0215 \times [\text{weight(kg)}]^{0.6469} \times [\text{height(cm)}]^{0.7236}$)

* Subject's age on Day 1 will be derived as (date of first dose – date of birth)/365.25.

The baseline disease characteristics will include:

- Duration of DMD in years (derived as, date of first dose – date of diagnosis +1)
- Age at Diagnosis (derived as, date of diagnosis – date of birth +1)

- Whether the subject has participated in any other DMD studies in 12 months prior to enrollment
- Participation in the FOR-DMD study

For the calculation of duration of DMD and age at diagnosis partial dates will be imputed using the earliest date that is consistent with the information available.

The baseline measurements will include:

- 6MWD (last measurement before dosing)
- NSAA total score
- NSAA linearized score
- 10 metre run/walk
- Time to stand
- PUL dimension and total scores
- PODCI sub-scales and global scores
- MRI parameters (the Vastus Lateralis and Soleus MRS fat fractions [MRS_FF_VL & MRS_FF_SOL] and water transverse relaxation times [MRS_T2_VL & MRS_T2_SOL])
- %MHCd positive (biopsy)
- Fibre diameter – mean
- Utrophin intensity – mean
- Utrophin heterogeneity score
- FEV₁ and FVC

The correlation between these baseline characteristics will also be tabulated. Age will be included.

In addition to summarizing the 6MWD as a continuous variable the number (%) of subjects in the following categories will be tabulated for the 6MWD and %-predicted 6MWD:

- 6MWD: < 300m, ≥300m and < 350m, ≥350m and < 400m, ≥400m
- <50% predicted, ≥50% and <70% predicted, ≥70 and <80% predicted, and ≥80% predicted

Similarly, in addition to summarizing the Vastus Lateralis and Soleus MRS fat fractions as a continuous variable the number (%) of subjects in the following categories will be tabulated:

- < 10%, ≥10% and < 20%, ≥ 20% and < 30%, ≥ 30% and < 40%, ≥40% and < 50%, ≥50% and < 60%, ≥60%.

Medical history data will be summarized by SOC and PT.

9.6 Efficacy Analyses

9.6.1 General

All analyses will be performed on the functional measures population.

Tabulations will be over all Cohorts 1 and 2 subjects and will not provide separate information for the two cohorts. Cohort 3 data will be summarized separately. In addition to the standard set of descriptive statistics summaries will also tabulate the number of subjects where their value has been imputed (see [Section 9.1](#)). The 95% confidence interval will also be included for the mean changes from baseline.

Box and whisker plots will display the Baseline, Weeks 12, 24, 36 and Week 48 data.

Mean changes from baseline, with associated 95% confidence intervals, will be plotted against visit. As visits in the extension phase will be included the plot will also include the n contributing to the visit.

The velocity of change per month will be assessed for specific endpoints. Velocities will be estimated using mixed effect models of the absolute values, including baseline. The model will include visit as a fixed effect term and subject as a random effect term. The following will be estimated along with 95% confidence intervals:

Velocity (12-B): (Week 12 – Baseline)/3

Velocity (24-12): (Week 24 – Week 12)/3

Velocity (36-24): (Week 36 – Week 24)/3

Velocity (48-36): (Week 48 – Week 36)/3

And

Velocity (24-B): (Week 24 – Baseline)/6

Velocity (48-24): (Week 48 – Week 24)/6

...

The following differences between velocities will also be estimated along with 95% confidence intervals:

Velocity (24-12) – Velocity (12-B)

Velocity (36-24) – Velocity (12-B)

Velocity (48-36) – Velocity (12-B)

And

Velocity (48-24) – Velocity (24-B)

...

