3.1 Sample Size Considerations

A suitable number of potential subjects will be screened in order that 55 subjects successfully meet the inclusion and exclusion criteria and continue into the Treatment Phase. Thirty subjects are expected to be enrolled in Cohort 1, approximately 10 in Cohort 2 and approximately 15 in Cohort 3. The sample size is not based upon statistical powering, but the number is considered to be sufficient to initially explore the endpoints and their relationship with SMT C1100 exposure.

Subjects who withdraw or who are withdrawn during the Treatment Phase may be replaced if the study has not yet reached full enrolment at the time of withdrawal. Subjects who withdraw or who are withdrawn due to an adverse event (AE) considered related to SMT C1100 will not be replaced.

Efforts will be made, in Cohorts 1 and 2, to balance the study populations and attempt to have at least 50% of boys with a fat: water fraction greater than or equal to 0.15. Efforts will also be made such that half of the boys are greater than or equal to 8 years of age. Such attempts will be made manually rather than via an automatic system; achieving these recruitment goals will be attempted but complete balance will not be enforced.

All subjects will be eligible to be rolled into the extension phase.

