4.0 Study Endpoints

4.1 Primary Endpoints

- Change from baseline to Weeks 12, 24, 36 and 48 in MRI leg muscle parameters (Cohorts 1 and 2)
- SMT C1100 and metabolite plasma concentrations at Weeks 1 (Days 1 and 7, as applicable (Cohorts 2 and 3 only)), 4, 8 (Cohorts 1 and 2 only), 12, 24, 36 and 48
- Safety data including:
 - Treatment emergent AEs

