5.3 Pharmacodynamic Assessments

5.3.1 Leg MRI/MRS (Cohorts 1 and 2)

The following leg muscle MRI/MRS parameters will be measured at Baseline and Weeks 12, 24, 36 and 48 during the first 48 weeks and then 6 monthly during the extension phase:

- MRS method
 - Fat Fraction in the Vastus Lateralis (MRS_FF_VL)
 - Fat Fraction in the Soleus (MRS_FF_SOL)

- Water Transverse Relaxation Time (1H2O-T2) in the Vastus Lateralis (MRS _T2_VL)
- Water Transverse Relaxation Time (1H2O-T2) in the Soleus (MRS _T2_SOL)
- 8 point Dixon method
 - Fat Fraction in the Vastus Lateralis (DIX_FF_VL)
 - Fat Fraction in the Soleus (DIX_FF_SOL)
 - Fat Fraction in the Biceps Femoris (DIX_FF_BFLH)
- MRI method
 - Proton Transverse Relaxation Time (T2) in the Vastus Lateralis (MRI_T2_VL)
 - Proton Transverse Relaxation Time (T2) in the Soleus (MRI_T2_SOL)
 - Proton Transverse Relaxation Time (T2) in the Biceps Femoris (MRI_T2_BFLH)

The MRS parameters from the Vastus Lateralis and Soleus are considered the primary MRI/MRS parameters for the study.

The fat fractions are reported as percentages, whilst T2 parameters are reported in ms.

Imputation will not be used for any missing data.

If a subject withdraws from the study prematurely they will also be assessed at the termination visit if not performed in the last 6 weeks.

Changes from baseline will be calculated.

The following velocities of change (change per month) will also be calculated for the MRS fat fraction measurements:

- Baseline to Week 12
- Week 12 to Week 24
- Week 24 to Week 36
- Week 36 to Week 48

And

- Baseline to Week 24
- Week 24 to Week 48

... and so forth when reporting the extension phase data

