9.7 Pharmacodynamics Analyses

9.7.1 Leg MRI/MRS (Cohorts 1 and 2)

All analyses will be performed using the Leg MRI/MRS population.

Tabulations will be over all subjects and will not provide separate information for the different cohorts.

Absolute values and changes from baseline will be summarized by visit for each of the 10 parameters. The 95% confidence interval will also be included for the mean changes from baseline.

The MRS fat fractions for the Vastus Lateralis and Soleus will be summarized by visit using a shift table from baseline. Marginal totals will be included. The categories used will be < 10%, ≥10% and < 20%, ≥ 20% and < 30%, ≥ 30% and < 40%, ≥40% and < 50%, ≥50% and < 60%, ≥60%.

Vastus Lateralis and Soleus MRS fat fraction and T2 parameters

The following outputs will only be presented for the Vastus Lateralis and Soleus MRS fat fraction and T2 parameters.

The velocities of change will be summarized using descriptive statistics. Velocities of change will also be analyzed using the methods described in [Section 9.6.1](#).

Individual subject data will be plotted against age as individual line plots (spaghetti plots) for each parameter.

Box and whisker plots will display the Baseline, Week 12, Week 24, Week 36 and Week 48 data.

Mean changes from baseline, with associated 95% confidence intervals, will be plotted against visit. As visits in the extension phase will be included the plot will also include the n contributing to the visit.

Week 12, 24, 36 and 48 changes from baseline will also be plotted against age on Day 1 and baseline, using different symbols to identify the Week. The Pearson correlation coefficient (for each week) will be footnoted on the plots.

The changes from baseline for parameters will be plotted against one another for Weeks 12, 24, 36 and 48 data. The week will be identifiable using different symbols. The Pearson correlation coefficients (for each week) will also be presented in the footnote of the plots.

The MRS fat fractions will be plotted against the corresponding MRI fat fractions and the MRS T2 values will be plotted against the corresponding MRI T2 values for the Vastus Lateralis and Soleus muscles. Absolute values will be plotted with different symbols used for each visit. The plot will be repeated for changes from baseline.

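### The velocity model's random subject intercept imposes equal variance and correlation across visits, so CIs for velocity differences and 12-week velocities are too wide if boys progress gradually at different rates

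*SAP*

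**What the plan says.** SAP 9.6.1 defines the method: "Velocities will be estimated using mixed effect models of the absolute values, including baseline". The terms are given in one sentence: "The model will include visit as a fixed effect term and subject as a random effect term". No random slope, residual covariance structure, robust standard error, degrees-of-freedom method or sensitivity model is named.

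The model yields 12-week and 24-week velocities with 95% intervals. For differences, the section adds: "The following differences between velocities will also be estimated along with 95% confidence intervals". Four main-phase differences are listed: each of the three later 12-week velocities minus the first, and the second 24-week velocity minus the first. The lists end in an ellipsis.

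SAP 9.7.1 carries the method to the vastus lateralis and soleus MRS fat fraction and T2, which SAP 5.3.1 calls primary: "Velocities of change will also be analyzed using the methods described in" Section 9.6.1. SAP 9.6.2 to 9.6.5 do the same for 6MWD, NSAA, 10-metre run/walk and time to stand. Leg scans continue beyond the main phase: "during the first 48 weeks and then 6 monthly during the extension phase". SAP 7.0 puts all available Cohort 1 and 2 data, extension included, in the main study report, and limits interim efficacy and pharmacodynamic data to Week 24.

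**The concern.** A random intercept allows boys to differ in level but not in rate. The plan gives reasons to expect different rates. Recruitment aims for a mix of ages and baseline fat fractions (SAP 3.1), two formulations are pooled (SAP 9.7.1), and a primary objective relates MRI change to plasma concentration (SAP 2.1).

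When rates differ, the single residual variance absorbs the slope differences and is then applied to every contrast. A velocity difference is a second-difference contrast in which a boy's own linear slope cancels, so its interval is charged for variation that it does not contain. In an uncontrolled study these differences are the contrasts that would show a change in progression, and the SAP estimates them only from this model.

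**Working it through.** There is no stated SD, power or interval width to reproduce, so the check is analytic, with simulation as confirmation.

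**Inputs from the documents.** About 30 + 10 = 40 boys (SAP 3.1: "Thirty subjects are expected to be enrolled in Cohort 1, approximately 10 in Cohort 2 and approximately 15 in Cohort 3"; Cohorts 1 and 2 are pooled). Visits at 0, 3, 6, 9 and 12 months, matching the SAP's divisors of 3 and 6. Interim visits at 0, 3 and 6 months.

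**Assumption.** Linear progression with random slopes. Let r = (SD of 12-month slope) / (residual SD σ), shown from 0.5 to 3.

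**Formulas, complete data.** For a contrast c over T visit times t:

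- Variance reported by the model: (c'c)·σ²(1 + k·r²)/n, with k = Sxx / [(T−1)·144]
- True variance: (c'c)·σ²(1 + h·r²)/n, with h = (c't)² / (144·c'c)
- Standard error ratio, model/true: √[(1 + k·r²)/(1 + h·r²)]

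**Values of k.** Weeks 0–48: Sxx = 36+9+0+9+36 = 90, so k = 90/(4·144) = 0.156. Interim: Sxx = 18, so k = 18/(2·144) = 0.0625.

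**Values of h.** All four velocity differences have c't = 0, so h = 0. For a 12-week velocity h = 9/(144·2) = 0.03125. For a 24-week velocity h = 36/(144·2) = 0.125.

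| Standard error ratio, model/true | r = 0.5 | r = 1 | r = 2 | r = 3 |
|---|---|---|---|---|
| Velocity differences, Weeks 0–48 | 1.02 | 1.08 | 1.27 | 1.55 |
| 12-week velocities, Weeks 0–48 | 1.02 | 1.06 | 1.20 | 1.37 |
| 24-week velocities, Weeks 0–48 | 1.00 | 1.01 | 1.04 | 1.06 |
| V(24-B), Week 24 interim | 0.99 | 0.97 | 0.91 | 0.86 |

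Example, differences at r = 2: √(1 + 0.15625·4) = √1.625 = 1.27. The precision is that of a correct analysis in about 40/1.625 ≈ 25 boys.

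**Simulation (n = 40, 2000 runs per scenario).**

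- V(48-24) − V(24-B) on Weeks 0–48: coverage of the nominal 95% interval is 96.2%, 99.0% and 99.7% at r = 1, 2, 3. Mean half-width is 0.137, 0.162 and 0.198 σ per month, against 0.129–0.130 with an unstructured covariance. The width ratio at r = 2 (0.162/0.130 = 1.25) is slightly below the standard error ratio because the random-intercept model uses more degrees of freedom.
- V(24-B) at the interim: coverage 93.6%, 92.4% and 90.9% at r = 1, 2, 3. With an unstructured covariance it is 94.6%, 94.6% and 94.4%.

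**Extension visits in the same fit.** The true standard error of V(48-24) − V(24-B) is √(6/36/40) = 0.065 σ per month. REML fits with half the boys reaching Week 72 and a quarter Week 96 moved the model's standard error as follows, with Week 0–48 data unchanged:

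| | r = 1 | r = 2 | r = 3 |
|---|---|---|---|
| Weeks 0–48 only | 0.069 | 0.082 | 0.099 |
| With staggered extension | 0.073 | 0.096 | 0.120 |
| Rise | 6% | 17% | 21% |

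The point estimate did not move, because every boy had complete Week 0–48 data. If every boy reached Week 96, k would be 429.4/(6·144) = 0.497, and the ratios to the true value would be 1.22, 1.73 and 2.34.

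**A case where the direction turns.** Suppose variation appears only as an abrupt loss at Week 48, with variance 9σ². The pooled residual is (4 + 9·0.8)/4 = 2.8σ². For V(48-36) − V(12-B) the ratio is √(2.8·4/13) = 0.93, slightly too narrow. For V(48-36) itself it is √(2.8·2/11) = 0.71.

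**The case against.** The strongest reply is that little turns on this. The study is exploratory and unpowered, no test or threshold is attached to the intervals, the main error is conservative, and the estimates themselves do not shift with complete data. If rates barely differ (r ≤ 0.5) the excess on Weeks 0–48 is about 2%. Per-boy velocities are also summarised descriptively, which gives a model-free check on each velocity. All of that stands, except that the descriptive check does not cover the velocity differences.

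A reader might infer four stronger things that the documents do not support:

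- **That all the velocity intervals miss 95% coverage.** The 24-week velocities are nearly right on Weeks 0–48 under gradual rate differences.
- **That Week 48 minus Baseline is badly covered.** It is not among the model contrasts in SAP 9.6.1. Mean changes from baseline have their own intervals in the descriptive summaries.
- **That interim and study-report error bars for main-phase contrasts would disagree on unchanged data.** The interim has no Week 36 or 48 efficacy or MRS data (SAP 7.0), so the data are not the same. Only the study report and later reports could show that effect.
- **That the full-extension multiples apply at the study report.** Extension entry is optional (Protocol 1.2) and follow-up will be staggered. The SAP also never says outright that one model takes all visits. SAP 7.0 and the ellipsis in 9.6.1 point that way, but the ellipsis may only extend the list of contrasts.

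**Conclusion.** The concern holds for a defined set of contrasts. As specified, the model imposes compound symmetry. Under gradual differences in rate, it overstates the uncertainty of the four velocity differences and the 12-week velocities, and it understates that of V(24-B) at the Week 24 interim.

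The size depends on r, which the documents do not give. For velocity differences on Weeks 0–48 it runs from negligible at r = 0.5 to 55% excess standard error at r = 3. Fitting extension visits jointly would add about 6–21% at r = 1–3 in the staggered example, and more as extension data accumulate; this part is conditional on an unstated choice of visits. Abrupt late loss can reverse the direction for V(48-36) − V(12-B). The harm is mainly lost precision on the contrasts that speak to changed progression, plus modest undercoverage at the interim.

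**What to change.** Amend SAP 9.6.1 to state:

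1. Week 0–48 velocities and differences are estimated from Baseline-to-Week-48 data only (at the interim, the visits to Week 24), with visit fixed, an unstructured within-subject covariance and Kenward-Roger degrees of freedom.
2. If that fit does not converge, use heterogeneous Toeplitz, and then a random intercept plus random slope, in that order.
3. Contrasts involving extension visits come from a separate model of all visits with a random intercept and slope, so that contrasts spanning Week 48 have a joint covariance.

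In the simulations, the unstructured analysis of V(48-24) − V(24-B) kept coverage at 94.6–96.2% and the half-width at 0.129–0.130 σ per month for r from 0 to 3, with or without extension visits.

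The cost is a short SAP change and a different covariance statement in the code. The downsides are 15 covariance parameters for about 40 boys (5·6/2), a small loss of degrees of freedom (at r = 0 the half-width goes from 0.127 to 0.129 σ per month), and possible use of the fallback. No new data are needed.
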